1 PROTOCOL REVISION HISTORY

Version	Date	Amended text	Description
V1.2_Feb 2024_GdA	12.2.2024 – 14.2.2024	Global	Accept changes Inserted variety of mood scales Amended PISCFs
V1.3_Feb 2024_GdA	20.2.2024	Global	Accept changes Update cortisol testing Change co-analysis to member checking
V1.4_Mar 2024_JA	1/03/2024	Aims and research team	Revised order of aims, Added [name] to research team, removed [name]
V1.5_Mar 2024_GdA_JA_NS	13/03/2024	Data collection	Insert final saliva sample collection protocol, added walking group schedule, added statistical analysis
V_1.6_13 Mar 2024_NS	14/03/2024	Global	Include further details on routines and structure of the walks. Edited reference list. Edited Table 1. Amended PICFs to include the PHQ9. Amended PICFs to include [name] on the consent forms. Included a list of appendices.
V_1.6_19 March 2024_NS	19/03/24	PICFs + NWG routines	Amended TCs job title, amended the NWG routines, changed PD's phone number
V_2.0_14 March 2024_NS	14/05/24	PICFs, survey, recruitment flyer, role of NS to include consent	Changes in response to GWHREC ethical review.

3 STUDY SUMMARY

Aims: This study aims to 1) evaluate the implementation of structured Nature Walking Groups (NWG) in mental health services, 2) identify the impact of facilitated nature contact for people living with severe and persistent mental health conditions, and 3) deliver evidence-based guidelines for service providers to implement and evaluate NWGs supporting future implementation and research.

Setting: Nature Walking Groups will be delivered in two sites in NSW – Orange (Non-Government Organisation) and Wollongong (Government led Mental Health Service).

Approach: The RE-AIM framework will be used to guide the collection of quantitative and qualitative data and their analysis.

Sample: Three groups of participants will be recruited; Group A – Intervention (n=40), Group B – non-walking group (n=40), and Group C – Nature Walking Group facilitators (n=10).

The intervention: A total of four NWGs over 12 months will be conducted in the two sites by the trained Nature Walking Group facilitators (Group C; n=10). Intervention participants (Group A; n=40) will participate in one NWG, receiving 1 hour per week in nature for a continuous period of 12 weeks (twelve walks per participant), while still also receiving treatment as usual (TAU). On each walk, facilitators will draw participant attention to one of the natural features and guide participants through stress reduction and mindfulness activities, lasting 3 to 10 minutes in duration. Individuals in Group B (control; n=40) will continue to receive TAU.

Data collection + procedures: Clinicians in both sites will be invited by site coordinators to undertake NWG facilitator training (Group C; n=10). Following training, facilitators will be invited to complete an Organisational Readiness Survey.

Information session will be held in each participating site, where researchers will recruit participants to either Group A (intervention) or Group B (non-walking). Participants in Group A and Group B will be invited to complete baseline surveys, and the first of three salivary samples to be collected at different intervals during the project for cortisol and Dehydroepiandrosterone (DHEA) testing (n=80).

Participants in Group A will then participate in the NWG intervention. Group A participants will be asked to complete a brief mood scale before and after each walk, and a researcher will complete ethnographic observations during the walk. Follow-up surveys will be completed by those in Groups A and B following the final walking group, and 3 months post-intervention.

Individuals who participated in the NWGs (Group A) will also be invited to a closing reflective focus group at the end of the twelfth walk to discuss their experiences of the groups. Follow-up phone interviews will be conducted with participants from Groups A to find out if they continued walking in nature and any reported longer term impact of the groups. Nature Walking facilitators (Group C) will be invited to participate in a focus group on their experiences delivering in the program.

De-identified aggregated client data to develop a descriptive profile of people using the services will be

provided by each participating site. Group A and B participants will be invited to participate in a member-checking workshop at the conclusion of data analysis. Any changes identified during these workshops will be incorporated into the final findings. Participants will be paid for completing measures as per the schedule listed at Section 10.3.

4 BACKGROUND

Forty-five percent of all Australians aged 16 to 85 years — 8.7 million people — will experience mental illness at some point in their life (AIHW, 2020). Mental illness and substance misuse are the second largest contributor (23%) of the non-fatal burden of disease in Australia (AIHW, 2019) with \$9.9 billion being spent on mental health in 2017–18 (AIHW, 2020). Given the prevalence and social and economic costs of mental illness, ensuring the access to, and effectiveness of mental health interventions is crucial.

The potential of nature contact for mental health recovery: There has been a growing interest in nature-based interventions, such as Nature Walking Groups (NWG), to prevent and address mental health symptoms (e.g., Marselle et al., 2019). Nature-based interventions have been shown to reduce negative mental health symptoms such as stress, anxiety and depression (Harvard Health Publishing, 2018; Marselle et al., 2019; Maund et al., 2019; Townsend & Weerasuriya, 2010). Contact with nature is associated with improvements in memory, cognition, and attention (Berto, 2014; Bratman et al., 2015) reduction in symptoms of depression and anxiety (Bloomfield, 2017; Grassini, 2022; Maund et al., 2019) lower stress levels (Corazon et al., 2018; Shunda et al., 2020; van den Berg & Beute, 2021) and healthy sleep patterns (Sia et al., 2020). Studies have also found that nature-based interventions such as forest bathing (Ideny et al., 2017), and community gardening (Howarth et al., 2020), resulted in greater levels of confidence, feelings of self-worth, happiness, feeling of safety, and sense of purpose and empowerment (O’Brien, 2018; Picton et al., 2018; Richardson et al., 2020; Sia et al., 2020). Nature exposure has also been linked with lower incidence of loneliness (Astell-Burt et al., 2022). When offered in groups, nature-based interventions create opportunities for social connections alleviating loneliness (Maund et al., 2019), which is one of the main indicators of mental and social wellbeing (Gierveld & Tilburg, 2006). Participating in nature-based interventions with others with similar lived experiences can enhance engagement, feelings of togetherness and belonging, and improve social skills (Maund et al., 2019; Richardson et al., 2020). Further, the physical exercise aspect of nature-based interventions can offer additional benefits to participants. There is an extensive body of literature describing the positive impact of physical activity on both physical and mental health (e.g., Ströhle, 2009; WHO, 2019). For example, a systematic review and meta-analysis of eight studies revealed that walking had a statistically significant, large effect on the symptoms of depression (Robertson et al., 2012). Similarly, according to the World Health Organization (2019), risk for depression can be reduced by up to 45% by increased physical activity.

Barriers to nature contact for people with enduring mental illness: The impact of enduring mental illness on people’s circumstances is significant. It limits many people’s ability to work, study and socialise resulting in poverty-related disadvantage such as poor housing, poor physical health, and social isolation (Migliorini et al., 2022). By middle-age, people with enduring conditions are likely to have experienced multiple episodes of illness and treatment. For these reasons, many people with enduring conditions prioritise improvement in social and functional outcomes over reduction in clinical symptoms (Barnett et al., 2022). People who regularly use green space (parks, gardens, bushland) and blue space (rivers, lakes, beaches) are more likely to have better mental, physical and social health than those who do not access these environments (Astell-Burt et al., 2020; Berto, 2014; Corazon et al., 2018). In terms of financial impact and efficiency, walking groups have the

potential to provide economic relief in several health-related areas. It is a cost-effective healthcare approach that can be used as a treatment alongside pharmacological and other non-pharmacological approaches (Hanson et al., 2015; Marselle et al., 2019). Despite the clear benefits of engaging in nature, individuals experiencing enduring mental illness and socio-economic disadvantage face multiple barriers to accessing these spaces, when compared to healthier, socio-economically advantaged individuals (Astell-Burt et al., 2014; Shanahan et al., 2019). These barriers restrict their ability to engage with and experience benefits from natural environments.

Preliminary research: This project is informed by a small preliminary study completed by the research team in 2022 where ten people participated in NWG as part of their mental health care. Group participants perceived them as rewarding and helpful, reducing their isolation and having a positive impact on their mental health. Moreover, they described usually experiencing difficulties accessing nature because they had no nature reserves near their housing, limited transport options, they could not afford park access fees and they had no experience with, or knowledge of nature reserves in the region (Olcon et. al., 2023). Nature Walking Group participants reported not wanting to walk on their own because of anxiety about transport logistics, getting lost, being alone and not having the motivation to deal with all those concerns (Olcon et. al., 2023). Further, our previous study demonstrated that clinicians supported NWGs but there is a lack of organisational capacity to implement them and concern about risks including the cost of the intervention (Tambayah et. al., 2022).

Based on these findings the proposed study considers the priorities, views, and values of both potential participants with enduring mental illness and healthcare providers in the way the NWGs are organised and run, and in the methods used achieve the project outcomes including evaluating organisational readiness, assessing the cost of implementation, and identifying the benefits of nature contact.

4.1 Aims

This research aims to explore the impact and the benefits of a NWG specific to the community mental health setting. The project will investigate the implementation and impact of walking and engaging with nature for participating consumers in two Australian community mental health services, one rural Non-Government mental health service (LikeMind) and one urban Government-led service (Illawarra Community Mental Health Service). Specifically, the project aims to:

1. Evaluate the implementation of structured NWGs in mental health services,
2. Identify the impact of facilitated nature contact for people living with severe and persistent mental health conditions,
3. Develop evidence-based guidelines for service providers to implement and evaluate NWGs supporting future implementation and research.

5 STUDY DESIGN

This study will employ a mixed methods design based on the RE-AIM framework to include the priorities, views and experiences of people with enduring mental illness and mental health care providers. As shown in Table 1, multiple methods of data collection and analysis will be used; wellbeing outcome measures – pre-, post-, and 3 month follow-up measures, salivary cortisol and DHEA testing pre- and post-intervention, ethnographic observation by a research assistant for each walking group, semi-structured interviews pre- and post-intervention, and member-checking workshops post analysis will be employed to determine the impact of the nature walking group intervention and identify contextual factors critical to its implementation in rural government and non-government health services.

5.1 Participating sites

The study will be conducted in two NSW locations – Orange (LikeMind, a Non-Government Organisation) and Wollongong (The Illawarra Community Mental Health Service, a Government Mental Health Service). Orange is classified as MMM3 – rural town, and Wollongong classified as MMM1 – major city . This will give us the opportunity to compare implementation in Non-Government Organisations and Government services and rural and urban sites.

Both sites support people with enduring and severe mental illness, such as major depressive disorder, bipolar disorder, and schizophrenia with an average age of 45 years (range 18–65). The ICMHS and LikeMind are in close proximity to either a variety of national parks and/or other green spaces. Therefore, the study will invite consumers presenting with a range of mental health conditions to participate.

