5.2 Training workshop (Group C)

NWG facilitators for each site and the research team will attend training and implementation workshops in February 2024 to provide training to facilitators which ensures adequate practitioner knowledge and skills, and practical guidance on nature routine implementation processes and the participant recruitment and data collection tools. Potential facilitators will be identified by site study co-ordinators (PD and TC) and invited to attend the training workshop.

Table 1 - Data collection methods and corresponding aims

		RE-AIM component				
		Reach	Efficacy	Adoption	Implementation	Maintenance
Aims	Data collection tool (planned data analysis approach)					
1. Implementation of NWG	Organisational readiness survey (Descriptive analysis)			x		
	Ethnographic observations during NWG (Thematic analysis)				x	
	Closing reflective focus group (Thematic analysis)				x	
	Facilitator post focus group (Thematic analysis)			x	x	
	De-identified site wide client data (Descriptive analysis)	x				
	NWG attendance records (Attendance ratio calculations)				x	
2. Impact of NWG	Pre/post and 3 month follow-up survey (Wilcoxon signed ranks)^		x			
	Pre-post salivary cortisol and DHEA testing (Change analysis)		x			
	Before and after mood scale (Change analysis)		x			
1 + 2. Impact and implementation	Phone interviews (Thematic analysis)		x		x	
3. Develop implementation and evaluation guidelines	Member-checking workshop (Thematic analysis)					x
	Site comparisons (Data triangulation)				x	x
	Data guide feedback (Guide draft reviewed)					x

^The Patient Health Questionnaire – Anxiety and Depression Scale is the primary outcome measure.

Key

RE-AIM Component	Reach	Identify characteristics, perceptions, and health service utilisation NWG participants, compared to control.
	Efficacy	Identify changes in nature connection, wellbeing, social isolation, quality of life and confidence/self-esteem for participants and control. Understand what worked for different groups and why.
	Adoption	Explore facilitator and management experiences and the implementation barriers and facilitators. Identify similarities and differences in NWG implementation and impacts between sites.
	Implementation	Monitor the implementation process and the experiences of participants.
	Maintenance	Ensure findings and recommendations reflect the lived experience of participants and inform the NWG implementation and evaluation guide.

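### Service type and rurality coincide across the two sites, so a site difference cannot be attributed to either one

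*Protocol*

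**What the plan says.** Protocol section 5.1 names the sites: "The study will be conducted in two NSW locations – Orange (LikeMind, a Non-Government Organisation) and Wollongong", the latter being the Government service. It then gives their remoteness class: "Orange is classified as MMM3 – rural town, and Wollongong classified as MMM1 – major city". Section 4.1 confirms the pairing, describing "one rural Non-Government mental health service (LikeMind) and one urban Government-led service".

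From this, section 5.1 concludes: "This will give us the opportunity to compare implementation in Non-Government Organisations and Government services and rural and urban sites".

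Section 5 states the purpose of the data collection as, in part, to identify "contextual factors critical to its implementation in rural government and non-government health services".

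Table 1 (under section 5.2) lists site comparisons under Aim 3, the development of guidelines, with data triangulation as the method. The key to that table says under Adoption: "Identify similarities and differences in NWG implementation and impacts between sites". The timeline in section 9 includes site comparisons in the data analysis. No section notes that service type and rurality coincide, and none limits how a site difference may be interpreted.

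**The concern.** Section 5.1 names two comparisons, NGO with Government and rural with urban, but two sites supply only one contrast. Because the sites differ on both factors at once, whatever is found in Orange and not in Wollongong could reflect the type of organisation, the rural setting, both, or something else particular to the site.

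This matters because the site comparison feeds Aim 3. A service provider using the guidelines could take a site difference as evidence about NGOs, or as evidence about rural services, and the study cannot say which. The phrase in section 5 adds to the risk, because it suggests that a rural government service is among those studied.

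**Working it through.** **The plan's own figure.** The protocol states no number for the site comparison. Its one computed figure is the sample size for the PHQ-ADS comparison of Groups A and B (section 7.1), checked here only to show that it stands apart from this point:

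- Difference: 22.76 − 16.08 = 6.68.
- Common SD: √((9.46² + 10.41²)/2) = 9.946.
- With 80% power and 5% significance (two-sided assumed, since sidedness is not stated), the noncentral t calculation gives 36 per group, with power 0.802. The normal approximation gives 35.
- Loss to follow-up: 72/(1 − 0.10) = 80.

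The stated 36 per group and 80 in total reproduce. Neither depends on the site comparison.

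**Inputs for the site comparison** (sections 4.1 and 5.1), with the number of sites in each cell:

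| | Rural | Urban |
|---|---|---|
| NGO | Orange (1) | none (0) |
| Government | none (0) | Wollongong (1) |

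Two of the four cells are filled, both on the diagonal.

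**What can be identified.** Let *m* be the level for an urban Government service, *a* the effect of being an NGO, *b* the effect of being rural, and *s* whatever else is particular to a site.

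- Orange: *m* + *a* + *b* + *s*(Orange)
- Wollongong: *m* + *s*(Wollongong)
- Difference: *D* = *a* + *b* + [*s*(Orange) − *s*(Wollongong)]

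Even if the site terms are set to zero, *D* = *a* + *b* is a single equation in two unknowns. The pairs (*a*, *b*) = (*D*, 0), (0, *D*) and (1.5*D*, −0.5*D*) all fit equally well. The share due to either factor therefore has no bounds unless the two effects are assumed to have the same sign.

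**The same in matrix form.** With columns for intercept, NGO and rural, the site rows are (1, 1, 1) and (1, 0, 0). The rank is 2 for 3 parameters, and the NGO and rural columns correlate at 1.00.

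**Does a larger sample help?** Section 5.3 plans 40 participants per site, and section 9 plans two walking groups of 10 per site, that is 20 walkers. With 1, 2, 20 or 40 rows per site the rank stays at 2.

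**What would change it.** Adding one site in an empty cell (an urban NGO or a rural Government service) raises the rank to 3. Additive effects would then be separable algebraically, but with one site per cell they would still be mixed with site effects.

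**Section 5 against section 5.1.** Section 5 speaks of "contextual factors critical to its implementation in rural government and non-government health services". The only Government service is in Wollongong, which section 5.1 classes as a major city and section 4.1 calls urban. Whether the word rural is read as covering both service types or only the first, the phrase includes a rural government service, and no such site is studied.

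**The case against.** The best defence is that the protocol does not set out to estimate these effects. Section 5.1 speaks of an opportunity, no aim or endpoint names service type or rurality as a factor to be estimated, and the method is triangulation across what section 5.3 calls case study sites. Interviews, observations and facilitator focus groups may let respondents say whether a barrier came from, for example, transport or organisational procedure. Section 4.1 already describes the sites accurately, and the key to Table 1 already speaks of differences between sites.

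Most of this stands, and it sets the weight of the point. A reader might infer that the protocol promises separate estimates of the two effects; its wording is softer than that. Qualitative accounts may suggest which factor mattered. But triangulating sources within two sites does not fill the empty cells, and section 5.1 presents both comparisons as available without any caveat.

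A reader might also infer that season and walking tracks are fully confounded with site. The documents do not show this. Section 10.1 plans a first round from about April to July and a second round at each site from about September, although sections 9 and 10.1 allow dates to vary. Section 5.5.3 has routines matched between sites and every walk graded 1 to 3.

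Nor do the documents support reading the guide as national, or as offering advice specific to rural government services. Section 4.1 describes guidelines for service providers in general, and the phrase in section 5 states a purpose, not a result.

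**Conclusion.** The point holds as a limit on interpretation. Service type and rurality coincide fully with each other and with site, so the two comparisons named in section 5.1 are one contrast. Only the combined difference is observed, and the share due to each factor is not identified. It would be tempting to say that the organisational share lies between 0% and 100% of the site difference, but that range assumes effects of the same sign, which nothing in the protocol supports.

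Separately, the reference in section 5 to rural government services conflicts with sections 4.1 and 5.1.

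The conclusion rests only on the protocol's own description of its two sites and on the absence of any further site. The consequence is confined to how site differences are read, chiefly in the Aim 3 guidelines. A descriptive comparison of Orange with Wollongong remains valid and useful. A reader might infer that the efficacy result is weakened too, but the primary PHQ-ADS comparison of Groups A and B and its sample size are unaffected.

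**What to change.** - **Section 5.1:** replace the sentence on comparison with a statement that the study describes and compares two case-study sites, one rural NGO and one urban Government service, and that differences will be reported as between-site differences, not attributed to organisation type or to rurality.
- **Section 5:** reconcile the reference to rural government services with the site descriptions in sections 4.1 and 5.1.
- **Table 1 and the guidelines:** add the same limit to the site comparisons row, and state it in the implementation guidelines wherever a site difference is discussed.

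This costs wording only. It needs no new data, site or analysis, and it narrows one claim. Separating the two factors would require further sites, including at least one in an empty cell, and this point does not ask for that.

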5.2 Training workshop (Group C)

NWG facilitators for each site and the research team will attend training and implementation workshops in February 2024 to provide training to facilitators which ensures adequate practitioner knowledge and skills, and practical guidance on nature routine implementation processes and the participant recruitment and data collection tools. Potential facilitators will be identified by site study co-ordinators (PD and TC) and invited to attend the training workshop.

Table 1 - Data collection methods and corresponding aims

		RE-AIM component				
		Reach	Efficacy	Adoption	Implementation	Maintenance
Aims	Data collection tool (planned data analysis approach)					
1. Implementation of NWG	Organisational readiness survey (Descriptive analysis)			x		
	Ethnographic observations during NWG (Thematic analysis)				x	
	Closing reflective focus group (Thematic analysis)				x	
	Facilitator post focus group (Thematic analysis)			x	x	
	De-identified site wide client data (Descriptive analysis)	x				
	NWG attendance records (Attendance ratio calculations)				x	
2. Impact of NWG	Pre/post and 3 month follow-up survey (Wilcoxon signed ranks)^		x			
	Pre-post salivary cortisol and DHEA testing (Change analysis)		x			
	Before and after mood scale (Change analysis)		x			
1 + 2. Impact and implementation	Phone interviews (Thematic analysis)		x		x	
3. Develop implementation and evaluation guidelines	Member-checking workshop (Thematic analysis)					x
	Site comparisons (Data triangulation)				x	x
	Data guide feedback (Guide draft reviewed)					x

^The Patient Health Questionnaire – Anxiety and Depression Scale is the primary outcome measure.

Key

RE-AIM Component	Reach	Identify characteristics, perceptions, and health service utilisation NWG participants, compared to control.
	Efficacy	Identify changes in nature connection, wellbeing, social isolation, quality of life and confidence/self-esteem for participants and control. Understand what worked for different groups and why.
	Adoption	Explore facilitator and management experiences and the implementation barriers and facilitators. Identify similarities and differences in NWG implementation and impacts between sites.
	Implementation	Monitor the implementation process and the experiences of participants.
	Maintenance	Ensure findings and recommendations reflect the lived experience of participants and inform the NWG implementation and evaluation guide.

